## SCHEMA

### Effect of Aspirin on Biomarkers of Barrett's Esophagus After Successful Eradication of Barrett's Esophagus with Radiofrequency Ablation

**1. Primary Endpoints:**

a) Difference in the change of tissue CDX2 mRNA levels in esophageal mucosa between participants taking aspirin and placebo at 12 months

**2. Secondary Endpoints**

a) Safety Profile (Toxicity Assessment) and tolerability of aspirin at 12 months.

b) Difference in the change of tissue CDX2 mRNA levels in esophageal mucosa between participants taking aspirin and placebo at 18 months

c) Differences in activation of NF- $\kappa$ B between groups by assessing levels of total and phospho-p65 and cytoplasmic to nuclear translocation of phospho-p65

d) Differences at 12 and 18 months in prostaglandin E2 levels

e) Differences in the expression of proinflammatory cytokines TNF $\alpha$ , IL-1 $\beta$ , IL-6, IL-10, IL-17A, IL-23

## 1. OBJECTIVES

**1.1 Primary Objectives** – We plan to conduct a randomized, double blind, placebo-controlled Phase II chemoprevention trial, investigating **whether supplementation with aspirin 325 mg/day for 12 months is safe and reduces the expression of CDX2 mRNA (a biomarker which has been associated with the risk of developing Barrett’s Esophagus [BE]) in comparison to placebo after successful radiofrequency ablation (RFA).**

**1.2 Secondary Objectives** – Secondary endpoints will assess safety at 12 months. Secondary endpoints will also assess differences in the expression of CDX2 at 18 months, **activation status of NF- $\kappa$ B** by assessing levels of total and phospho-p65 and cytoplasmic to nuclear translocation of phospho-p65 which is likely to be affected by aspirin. Additional secondary endpoint markers will be the prostanoid marker, prostaglandin E2, and prostaglandin synthases, which are known to respond to aspirin and to correlation with clinicopathological factors in the esophageal cancer PGE2 was previously shown to be reduced in Barrett’s mucosa in response to a combination of acid inhibition and high-dose (but not low dose) aspirin. Furthermore, differences in the expression of proinflammatory cytokines known to induce activation of NF $\kappa$ B, i.e., **TNF $\alpha$ , IL-1 $\beta$ , IL-6, IL-10, IL-17A, IL-23** will be measured. These inflammatory mediators have been implicated in the pathogenesis of Barrett’s Esophagus and esophageal adenocarcinoma. **Recurrent Barrett’s Esophagus** (at 12 and 18 months) will be ascertained completely and accurately. **While we will not have sufficient power to assess differences in histological recurrence of BE during the short course of the study, we will examine this as an exploratory secondary endpoint. This study will generate data designed to lead to the submission of an adequately powered multi-center prospective chemoprevention trial with histologic recurrence of BE after RFA as the clinically relevant primary endpoint.**

## 2. BACKGROUND

### 2.1 Study Disease: Barrett's Esophagus (BE)

The incidence of adenocarcinoma of the esophagus (EA) has increased dramatically over the past three to four decades in western countries. This increase has occurred in all race and gender groups, most dramatically in white males. According to data from the National Cancer Institute's Surveillance, Epidemiology and End Results (SEER) program, the incidence of esophageal adenocarcinoma (EAC) in white males rose from 0.8 per 100,000 in 1973 to 5.4 per 100,000 in 2002, a near-annual increase of 8% . Barrett's esophagus (BE) is being increasingly recognized in western countries and is widely considered the major risk factor for EAC (1). Activation of signaling pathways may facilitate the healing of reflux-damaged squamous cells through metaplasia (manifested as BE). Identifying these pathways could provide molecular targets for chemoprevention to prevent Barrett’s Esophagus from recurring in patients who have undergone endoscopic ablation of Barrett’s epithelium. Molecular, biochemical, and immunohistochemical studies have focused on potential pathways and markers that may result in Barrett's metaplasia and subsequent transformation and progression to adenocarcinoma (1-4). Cancers are believed to arise through the development of genetic instability and clonal expansion driven by selection for mutations in cancer genes. A combination of genetic instability and clonal expansion is associated with progression to adenocarcinoma in BE. Chronic exposure to both acid and bile in the gastroesophageal refluxate promotes damage and inflammation in the esophageal epithelium which may trigger these changes (3). Within the epithelial cells, the combination of reactive oxygen species (ROS) damage, alterations in DNA methylation, activation of the NF $\kappa$ B signaling pathway by cytokines and the acid/bile refluxate contribute to activation of target genes that further amplify inflammation and promote intestinal differentiation (5-7). These changes are associated with biological and morphological changes which are manifested as “biomarkers” which are associated with disease progression. Cdx homeotic genes of the

[figure not shown]
para-homoeobox family appear to direct the formation of simple columnar epithelia, and the metaplastic epithelium of BE express CDX messenger RNA and protein (5, 8). **Existing data from our group (see below) suggest that acid and bile salts induce CDX2 in esophageal squamous cells from patients with BE, but not from GERD patients without BE (8).** These differences may underlie the development of BE and could serve to predict development of metaplasia both de novo and after ablation.

## 2.2 Study Agent: Aspirin 325 mg/day for 12 months

Endoscopic ablative techniques such as radiofrequency ablation (RFA) have provided an alternative to surgery in treating high-risk lesions including high grade dysplasia associated with BE (9,10). Long-term follow-up has, however demonstrated recurrence of BE after RFA ranging from 8% to 25% (9-12). Long-term use of nonsteroidal anti-inflammatory drugs (NSAIDs), especially **aspirin**, has been associated in observational studies with a decreased risk of EAC (OR 0.54 in one pooled analysis) and a decreased risk of neoplastic progression in BE (13). NSAIDs may be especially associated with decreased EAC risk in individuals with high-risk markers predictive of conversion to EAC (4). Aspirin may play a protective role against the development of EAC by inhibiting chronic inflammation and NFkB-dependent transcriptional induction of CDKN2A and prostaglandin biosynthesis genes which have been shown to contribute to carcinogenesis (4, 5,13). Aspirin-induced suppression of NF-KB target genes is significant, because acid and bile salts activate NF-kB to induce CDX2, which has been recently linked to the development of Barrett’s metaplasia (8). Using PGE2 concentrations as a surrogate for NF-KB activation levels, aspirin (325 mg/day) in combination with acid inhibition significantly reduces NF-KB activation in esophageal tissue from individuals with BE (14) Moreover, aspirin has been used extensively in chemoprevention trials of gastrointestinal and other forms of neoplasia with an acceptable safety profile (15).

## 2.3 Rationale

**CDX2 and the Development of Intestinal Metaplasia:** Metaplastic conditions like BE are associated with a high rate of cell turnover that may be stimulated by chronic inflammation (16). The continuous cycle of injury and repair that accompanies chronic inflammation predisposes to alterations in the pattern of gene expression by the epithelial cells. Metaplasias occur when such alterations affect homeotic genes, like CDX2, that control tissue phenotypes. In one study of esophageal biopsy specimens taken from patients with BE, CDX2 expression levels were approximately 400 times higher in the Barrett’s metaplasia than in the normal esophageal squamous epithelium, in which the levels were almost undetectable (17). In fact, CDX2 has been implicated as the “master switch” in the formation of Barrett’s metaplasia. In a rat model of reflux esophagitis and intestinal metaplasia, basal cells in the esophageal squamous epithelium begin to express CDX2 prior to the development of intestinal metaplasia suggesting that CDX2 expression precedes the development of Barrett’s metaplasia and that GERD may initiate the development of intestinal metaplasia by increasing CDX2 expression in esophageal stem cells (18,19).

### Reflux Esophagitis and the Induction of CDX2:

There are at least two ways in which GERD might induce CDX expression in the esophagus: 1) Certain components of the refluxed gastric juice (e.g. acid, bile salts) stimulate CDX expression by esophageal stem cells or 2) Esophageal inflammation (reflux esophagitis) stimulates CDX expression by esophageal stem cells. Following ablation of BE, re-epithelialization by squamous cells is favored in the setting of acid suppression

whereas recurrent Barrett's epithelium occurs when acid suppression is inadequate (20,21). Thus, it is recommended that patients with BE should take PPIs as a means to prevent recurrence in the setting of ongoing reflux (22). However, PPIs do not correct the underlying reflux diathesis and *Barrett's patients who take PPIs still have frequent reflux of weakly acidic (pH 4-7) material (including bile acids)* (23). Perhaps this is why a substantial proportion of patients with BE have recurrence of intestinal metaplasia following RFA. Differences in gene expression profile within the regenerated squamous epithelium may predict which Barrett's patients recur and subsequently require recurrent endoscopic intervention. We have previously shown that esophageal squamous epithelial cells from GERD patients with BE increase the expression and activation of CDX2 in response to exposure to acid, bile salts, and the combination of both. **In contrast, esophageal squamous cells from patients who have GERD without Barrett's Esophagus fail to induce CDX2 expression in response to any of these exposures** (8). Our preliminary data demonstrate that compared to squamous cells from Barrett's patients, squamous cells from GERD patients exposed to acid and bile salts exhibit less phosphorylation of IKK $\alpha/\beta$  and IKB, and less nuclear translocation of p50. Unlike the squamous cells from Barrett's patients, furthermore, the GERD squamous cells show no nuclear translocation of p65, and p50 does not bind their CDX2 promoter. In squamous cells from Barrett's patients, knockdown of p65 by siRNA inhibits the induction of the CDX2 promoter suggesting that nuclear translocation of p65 is functionally relevant for the induction of CDX2 in response to acid and bile salts. These data suggest that phenotypic differences among patients in how the NF-KB pathway in their esophageal squamous cells responds to gastric reflux might determine whether they develop Barrett's metaplasia. We propose to investigate the chemopreventive potential of aspirin, which has been shown to affect the expression and activation of NF-KB related pathways in the esophagus. CDX2 expression will serve as a surrogate marker of recurrence of Barrett's metaplasia after RFA.

### 3. SUMMARY OF STUDY PLAN

#### 3.1 Target Population

- Age  $\geq$  18 years
- Known diagnosis of histologically-confirmed BE with or without dysplasia (as defined by the presence of specialized columnar epithelium anywhere in the tubular esophagus with  $\geq$  1 cm of circumferential or non-circumferential involvement of specialized columnar epithelium) requiring radiofrequency ablation.
- Documentation of complete ablation of BE after radiofrequency ablation on two endoscopic examinations at least 3 months apart (including no evidence of BE on surveillance and biopsies). Completion of ablation should have occurred no greater than 36 months prior to randomization.

#### 3.2 Sample Size and Duration of Accrual

This is a randomized, double-blind placebo controlled study with 2 intervention arms. We plan to enroll up to 20 participants per group.

#### 3.3 Intervention Arms

Participants who have successfully completed radiofrequency ablation for BE with or without dysplasia and who have been histologically-confirmed to be free of Barrett's will be randomly assigned to a 12 month intervention with:

Arm A - aspirin 325 mg PO QD

Arm B – aspirin placebo QD

All participants will take proton pump inhibitor in the FDA approved healing dose as clinically

indicated (omeprazole or S-omeprazole 40 mg twice daily, lansoprazole 30 mg twice daily or equivalent).

Participants will continue study agent up to the day of the 12-month endoscopic assessment (see below).

#### Study Assessments

Endoscopic examination of the esophagus will be performed as part of a clinically prescribed protocol for patients undergoing radiofrequency ablation for BE. Participants who have documentation of complete ablation on at least 2 separate occasions 3 months apart will be eligible to participate in the study. An endoscopy performed for a second demonstration of ablation may serve as a qualifying exam. Clinically indicated biopsies will be performed using the Seattle protocol and sent for local Pathology assessment. Additional study biopsies will be performed at baseline and at 12 and 18 months in locations 1 cm above the gastroesophageal junction, midway through an area defined by the length and location of the pre-ablation Barrett's segment, and 2 cm above the upper extent of the original Barrett's segment. Standardization of endoscopic techniques, assessment of landmarks and tissue procurement methods across Participating Organizations will be achieved through a series of pre-trial discussions with the Protocol Lead Investigators. Details of the biopsy protocol are provided in Section 7.6.1 and 7.6.2.

All participants will have a telephone interview at Month 1 regarding symptoms possibly related to the agent, illnesses, doctors' visits, hospitalizations, mediations (including over the counter medications), and compliance with study tablets. Adherence with the study medication will be discussed and reinforced; pill diary will be reviewed.

All participants will have a telephone interview and/or be contacted by mail every 3 months regarding symptoms possibly related to the agent, illnesses, doctors' visits, hospitalizations, mediations (including over the counter medications), and compliance with study tablets.

Participants will undergo a clinically indicated surveillance EGD at 12 months following randomization at which time clinically indicated surveillance biopsies and research biopsies will be obtained. End of treatment questionnaires and SF-36 Health Surveys, physical exam and laboratories will also be performed.

Participants will be followed off aspirin or placebo for an additional 6 month period (with an interval phone interview at 13 months post-randomization). Participants will undergo a clinically indicated surveillance EGD at 18 months following randomization at which time clinically indicated surveillance biopsies and research biopsies will be obtained.

Expression of CDX2 mRNA and differences in the activation status of NF- $\kappa$ B will be analyzed in the laboratory of [name] at the Center for Esophageal Research, Baylor Scott & White Research Institute, Dallas, TX. Prostaglandin E2 levels and expression of pro-inflammatory cytokines will be assessed in the laboratory of [name] Ph.D. at the University of Texas MD Anderson Cancer Center.

## 4. PARTICIPANT SELECTION

### 4.1 Inclusion Criteria

- 4.1.1 Age  $\geq$  18 years
- 4.1.2 Known diagnosis of histologically-confirmed BE with or without dysplasia (as defined by the presence of specialized columnar epithelium anywhere in the tubular esophagus with  $\geq$  1 cm of circumferential or non-circumferential involvement of specialized columnar epithelium) requiring radiofrequency ablation.
- 4.1.3 Documentation of complete ablation of BE after radiofrequency ablation on two endoscopic examinations at least 3 months apart (including no evidence of BE on surveillance biopsies) as determined by the pathologist at each site. Completion of ablation should have occurred no greater than 36 months prior to randomization.
- 4.1.4 The effects of the candidate chemoprevention agents on the developing human fetus remain incompletely defined. For this reason, persons of childbearing potential and men must agree to use adequate contraception (hormonal or barrier method of birth control; abstinence) prior to study entry and for the duration of study participation. Should a participant become pregnant or suspect she is pregnant while participating in this trial, she should inform the research personnel and her clinical care provider immediately.
- 4.1.5 Willingness to provide tissue samples for research purposes.
- 4.1.6 No chronic use of aspirin or NSAIDs or selective COX-2 inhibitors during one month prior to randomization. Chronic use is defined as any aspirin or NSAID use on  $\geq$  7 days during one month preceding the beginning of randomization.
- 4.1.7 Normal organ and marrow function, as defined below, based on laboratory studies obtained  $\leq$  45 days prior to randomization:
  - Hemoglobin .....  $\geq$ 10 g/dL or Hematocrit  $\geq$ 30 %
  - Leukocyte count.....  $\geq$ 3,000/microliter
  - Platelet count .....  $\geq$ 100,000/microliter
  - Absolute neutrophil count.....  $\geq$ 1,500/microliter
  - Creatinine.....  $\leq$ 2.5 x institutional ULN
  - OR GFR.....  $>$ 30ml/min/1.73m^2
  - Total bilirubin .....  $\leq$ 2 x institutional ULN
  - AST (SGOT).....  $\leq$ 2.5 x institutional ULN
  - ALT (SGPT) .....  $\leq$ 2.5 x institutional ULN
- 4.1.8 A negative serum pregnancy test at Baseline, but within 21 days of Randomization, for persons of childbearing potential only.
- 4.1.9 ECOG performance status  $\leq$  2 (see Appendix A).
- 4.1.10 Ability to understand and the willingness to sign a written informed consent document. A Legally Authorized Representative (LAR) may sign Informed Consent for persons who do not have the capacity to legally consent to take part in the study.

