### 4.2 Exclusion Criteria

- 4.2.1 Inability to abstain from NSAID (including aspirin) and selective COX-2 inhibitor therapy at the time of randomization through the completion of the study (the study period is defined as baseline to exit endoscopy at 18 months after randomization which defines the completion of the study). Participants may take Tylenol and Non-NSAID pain relievers.
- 4.2.2 Current or planned use of anticoagulant drugs such as: warfarin, heparin, low molecular weight heparin, Plavix, or Aggrenox throughout the course of the study.
- 4.2.3 Individuals taking the drugs listed below may not be randomized unless they are willing to stop the medications (and possibly change to alternative non-excluded medications to

treat the same conditions) no less than 1 month prior to starting aspirin or placebo on this study. Consultation with the participant's primary care provider will be obtained prior to stopping any agent. The use of the following drugs or drug classes is prohibited during aspirin/placebo treatment:

NSAIDs: such as aspirin, Naprosyn, ketorolac and others NSAIDs

COX-2 inhibitors: such as Celecoxib, Rofecoxib

Valproic acid

Sulfinpyrazone

Probenecid

Corticosteroids (other than short-term use defined as less than 2 weeks or prn use of an inhaler less than twice per month)

Platelet aggregation inhibitors, except in a monitored antithrombotic regimen

Methotrexate (MTX)

Vaccines containing live viruses

Ginkgo

- 4.2.4 Individuals with uncontrolled renal insufficiency or renal failure.
- 4.2.5 Participants with fundoplication within the past year, bariatric surgery or any other major upper GI surgery. Fundoplication more than one year ago will not be grounds for exclusion. Cholecystectomy will not be grounds for exclusion.
- 4.2.6 History of invasive cancer diagnosis  $\leq$  12 months prior to randomization, excepting non-melanoma skin cancer. Patients with T1a adenocarcinoma of the esophagus arising in the setting of Barrett's esophagus are eligible for enrollment in the trial.
- 4.2.7 History of cancer treatment  $\leq$  12 months prior to randomization, excepting hormonal therapy (except treatment for non-melanoma skin cancer or carcinoma-in-situ of the cervix).

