#### 6.1.1 Rescue Medication:

Participants will be allowed to take acetaminophen in clinically indicated doses for headache or pain, but will not be allowed to take aspirin or other NSAIDS during the entire study period (baseline to 18 months after randomization).

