## 7.2 Baseline Testing/Prestudy Evaluation

### 7.2.1 Screening

Eligible participants will be identified from patients undergoing or who have undergone radiofrequency ablation for BE and are participating in or will participate in an ongoing surveillance program. Potentially eligible participants will be identified through database/charts/clinic lists prior to Baseline Visit. A letter may be mailed to potentially eligible participants introducing the study to the patients. If the Site chooses to utilize a letter, the letter will be signed by the Site PI who is familiar to the patient as the doctor following their medical condition. If the Site PI is not the patient's physician who is treating their BE, the letter will be co-signed by the physician who is familiar to the patient. To facilitate screening, the Study Coordinators are advised to call potential participants and introduce the study over the phone, as well as administer the screening questionnaires. However, the study team may choose to administer the questionnaires in person when the participant is seen at the clinic. Screening to identify potentially eligible participants takes place prior to obtaining Informed Consent. The following questionnaires will be administered during Screening:

- Baseline history assessment questionnaire, to include a review of cancer history and previous medical history, previous surgery, chemotherapy, radiation, and other cancer-directed therapy history, family history, demographic information, including age and race, history of allergies or intolerance to aspirin, aspirin containing products or NSAIDs.
- Symptom Assessment Questionnaire, to include a review of the following symptoms: gastrointestinal bleeding, hematemesis, hematochezia, melena, abdominal pain/cramping, heart burn, irregular heart rate/palpitations, chest pain, shortness of breath, edema, itching, constipation, diarrhea, headache, dizziness, drowsiness, lightheadedness, vertigo, easy bruising/bleeding.
- Use of concomitant medications will be collected.

If the participant is found to be potentially eligible for the study, a Baseline visit will be scheduled.

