**Notes:**

- Any screen failed participant who is deemed ineligible based on medical history, physical exam, laboratory values, pregnancy test or persistence of BE at qualifying exam after consent is obtained will need to have a screen failure case report form completed. Information will be recorded on the appropriate CRF(s) up until the point at which the participant was found ineligible and screen failed.
- Participants who are ineligible due to regular aspirin or NSAID use at the time of screening may be reevaluated after refraining from aspirin or NSAID use for one month.
- If a pregnancy is discovered after Randomization, instruct the participant to stop taking drug, take participant off-study, complete the Off-Study CRF, follow the pregnancy to term and complete the Outcome of Pregnancy CRF.

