### 7.2.3 Randomization

Subjects meeting the criteria outlined above and whose standard of care surveillance biopsies document absence of residual Barrett's metaplasia or dysplasia will be eligible for randomization which will take place within 45 days of the qualifying endoscopy. The randomization visit may be in person or by phone.

- Randomization: Once registration is complete, eligibility has been confirmed and eligibility CRF is entered into the web application, participants will be assigned a randomization number pre-generated by the database. Participants will be randomized to receive either active agent (aspirin 325 mg) or placebo. Both the participant and the investigator will be blinded to the agent.
- Symptom assessment.
- Concomitant medications.
- Randomized participants will receive a 3-month supply of study agent (90 pills plus 10 additional pills). The drug supply may be mailed to the participant or given to the participant in person.
- Review pill diary and pill intake instructions with the participant. Participants must be instructed to take at least 3 months of pills from their first bottle prior to starting the next bottle and to record the date that the new bottle is started.
- Assess adverse events.

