## 8. CRITERIA FOR EVALUATION AND ENDPOINT DEFINITION

### 8.1 Primary Endpoint

The **primary endpoint** of the study will be **differences in the change of CDX2 mRNA levels from baseline to 12 months post-randomization in esophageal squamous tissue between participants taking aspirin supplementation versus those taking placebo. CDX2 mRNA levels will be compared at baseline versus at 12 months within each participant, and the change in CDX2 mRNA levels compared between participants taking aspirin participants taking placebo (similar comparisons will be made for differences in the change of secondary biomarkers-see below).** Our *rationale* to use this biomarker is based on the direct link between aspirin, chronic inflammation, and the downregulation of NF-kB-induced downstream target genes among which is CDX2 (4,5,8). Total RNAs will be isolated from squamous and neosquamous mucosal biopsy specimens using Trizol (Invitrogen, Carlsbad, CA) and quantitated by spectrophotometry. Reverse transcription will be performed using QuantiTect Reverse Transcription kit (Qiagen, Valencia, CA) per manufacturer's instructions. Real-time PCR for CDX2 mRNA will be carried out using rapid cycling with the StepOnePlus Real-Time PCR System and SYBR mix (Life Technologies, Carlsbad, CA) using previously published CDX2 primer sequences (8).

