## 10.2 Collection and Handling Procedures

### Research Mucosal Biopsy Specimens

[figure not shown]
Esophageal mucosa biopsy techniques have been described in Section 7. Types of assay conducted for each biopsy specimen are described in Section 8. Research biopsies will be obtained at baseline (after consent but prior to randomization), at 12 months and at 18 months as described in Section 7.

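### The one-month aspirin/NSAID/COX-2 inhibitor rule is counted back from randomization or first dose, not from the baseline biopsy taken up to 45 days earlier, so a baseline sample with little or no washout is permitted

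*Combined protocol and SAP*

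**What the plan says.** Two clauses set the drug-free month. Section 4.1.6 requires "No chronic use of aspirin or NSAIDs or selective COX-2 inhibitors during one month prior to randomization" and defines chronic use as use on 7 or more days in that month. Section 4.2.3 requires users of listed drugs, including aspirin, NSAIDs and COX-2 inhibitors, to stop "no less than 1 month prior to starting aspirin or placebo on this study".

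The baseline sample is dated differently. Section 10.2 states: "Research biopsies will be obtained at baseline (after consent but prior to randomization), at 12 months and at 18 months". Section 7.2.2 places these biopsies at the qualifying endoscopy. Section 7.2.3 makes participants with clear histology "eligible for randomization which will take place within 45 days of the qualifying endoscopy".

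The primary endpoint depends on that sample. Under section 8.1, "CDX2 mRNA levels will be compared at baseline versus at 12 months within each participant", and the change is then compared between arms. Section 10.2 assigns biopsies from the same endoscopy to p65, PGE2 and the cytokines.

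Three other provisions bear on the gap:
- Section 6.1.1: participants "will not be allowed to take aspirin or other NSAIDS during the entire study period (baseline to 18 months after randomization". This runs forward from baseline.
- Section 7.2.1: medications are collected at screening, and then "If the participant is found to be potentially eligible for the study, a Baseline visit will be scheduled".
- Notes to section 7.2.2: people ineligible at screening because of regular aspirin or NSAID use "may be reevaluated after refraining from aspirin or NSAID use for one month".

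**The concern.** A washout for a change-from-baseline biomarker should end at the baseline sample. Here it ends at randomization or first dose, and the sample may come up to 45 days before randomization. By the plan's own rationale this could matter. Section 2.2 reports that aspirin 325 mg/day with acid inhibition lowered NF-kB activation in esophageal tissue, using PGE2 as the surrogate. Sections 8.1 and 13.4 place CDX2 downstream of that pathway. A participant biopsied on drug may therefore lack an untreated baseline for CDX2, and the same applies to PGE2, which section 8.2.4 describes as responsive to aspirin.

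If the drug lowers the baseline value, that participant's change to 12 months is too large by the same amount. Scatter in the changes rises, and the mean change in each arm moves upward. With 18 evaluable participants per arm, there is little room for avoidable variation.

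**Working it through.** **1. Dates.** Take a month as 30 days, and let t be the number of days from baseline biopsy to first dose. The drug-free days before biopsy that 4.2.3 guarantees are max(0, 30 − t).

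| t (days) | Guaranteed drug-free days at biopsy |
|---|---|
| 14 | 16 |
| 21 | 9 |
| 30 or more | 0 |

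If randomization and first dose fall on the same day and the biopsy is at the 45-day limit, the biopsy precedes the start of the required month by 45 − 30 = 15 days (14 to 17 days for a month of 31 to 28 days). Section 4.1.6 is looser than 4.2.3, since it tolerates up to 6 days of use.

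**2. Does another clause close the gap?** Suppose a person takes an NSAID course after screening, stops just before the biopsy, and is randomized 40 days later.
- 4.1.6: no use in the month before randomization. Met.
- 4.2.3: stopped more than a month before first dose. Met.
- 4.2.1: concerns inability to abstain from randomization onward, with the study period starting at baseline. Met.
- 6.1.1: no use from baseline onward. Met.
- 7.2.2 note: addresses regular use at screening. Not triggered.

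The schedule of events and section 7.2.2 record medications again at the Baseline visit, so the use would be seen, but no rule stops the biopsy.

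**3. The plan's power.** Section 13.4 assumes a difference in change of 20, SD 20, 18 per group, and a two-sided 5% two-sample t-test. The noncentrality is (20/20) × √(18/2) = 3 with 34 degrees of freedom, giving power of 83.0%. The stated 83% reproduces.

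**4. Illustration of lost precision.** The documents give neither the fraction f biopsied without washout nor the fall s in their baseline value. Both are assumptions. The SD of change becomes √(400 + f(1 − f)s²), and each arm's mean change shifts by f × s.

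| s | f | SD of change | Power, 18 per arm | Within-arm shift |
|---|---|---|---|---|
| 10 | 5% | 20.12 | 82.6% | +0.5 |
| 10 | 10% | 20.22 | 82.2% | +1.0 |
| 10 | 25% | 20.46 | 81.3% | +2.5 |
| 20 | 5% | 20.47 | 81.3% | +1.0 |
| 20 | 10% | 20.88 | 79.7% | +2.0 |
| 20 | 25% | 21.79 | 76.3% | +5.0 |

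The expected shift f × s is the same in both arms because exposure precedes allocation, so it cancels from the difference between arms.

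**5. Handling exposed participants in the analysis.** In simulations of 20,000 trials with s = 20, a covariate for exposure gives power of about 81% to 82% at f = 5%, 10% and 25%. Excluding exposed participants gives about 81%, 78% and 69%.

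**The case against.** The strongest reply is that the sequence of visits already does most of the work. Medications are taken at screening, only potentially eligible people are booked for the Baseline visit, and regular users are ineligible until they have been off drug for a month. Read in that order, a habitual user finishes the month before the endoscopy. This largely stands. A reader might infer that habitual users will routinely be biopsied on drug, and the documents do not support that. What remains is that the note does not tie the month to the endoscopy and does not reach use that begins after screening.

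The second reply concerns size, and it stands in full. Section 13.4 says that aspirin's effect on tissue CDX2 is not known, and it assumes that aspirin prevents a rise (100 to 100, against 100 to 120 on placebo), not that it lowers a baseline. A 20-unit shift would credit prior use with the whole planned 12-month difference. Sections 1.2 and 8.2.4 add that PGE2 fell with high-dose but not low-dose aspirin, so low-dose users may show no shift at all. The planned SD of 20 may already contain some of this variation. A reader might infer from the table above that the trial is underpowered. It does not show that, because f and s have no source in the documents.

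Third, an exposure covariate may have little to work on. With 36 evaluable participants and 5% exposed, about 2 are flagged, and the binomial probability of none or one is about 46%. This also stands.

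Finally, anchoring to randomization spares people from stopping aspirin before histologic eligibility is known. That is a real advantage, but it does not protect the sample on which the primary endpoint is built.

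**Conclusion.** The rule has the wrong anchor for its purpose. As written, a participant can comply with every clause and still give a baseline biopsy with little or no washout. That conclusion rests on dates alone.

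The consequence is modest and its size is unknown. The arm comparison is not biased on average. A reader might infer bias in the primary result, but use before the biopsy cannot depend on allocation. What is exposed is some precision, chance imbalance in small arms, and within-arm changes that may be shifted. The illustrative ranges (power of 82.6% to 76.3% against 83.0%; within-arm shift of 0.5 to 5 units against a planned placebo rise of 20) depend entirely on the assumed 5% to 25% exposed and 10 to 20 unit fall. They should not be read as estimates. This is a cheap improvement to the protocol. It covers aspirin, NSAIDs and COX-2 inhibitors before the biopsy only, and says nothing against the timing for the other drugs in 4.2.3.

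**What to change.** - In 4.1.6, and in 4.2.3 for aspirin, NSAIDs and COX-2 inhibitors only, count the existing month back from the qualifying endoscopy with research biopsies and continue it to randomization. Leave the other 4.2.3 drugs as they are.
- Make the 7.2.2 note say that the month off must be completed before that endoscopy.
- Obtain consent, and the primary care consultation that 4.2.3 already requires, before any stop that the study asks for. Consent is now taken at the Baseline visit, so for these participants it would have to come earlier.
- Do not delay a clinically needed endoscopy. If it cannot wait, record the last-dose date from the concomitant-medication CRF, which already collects start and stop dates where known.
- Optionally, flag use of these drugs in the 30 days before biopsy and run one supportive analysis with the flag as a covariate, keeping everyone. It is informative only if more than a few are flagged. Do not exclude flagged participants.

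Sample size and the primary test do not change. The cost is wording in three places and an earlier consent step for some participants. The downside is that some users stop up to about 45 days sooner, before histologic eligibility is known, and some of them will then fail screening.
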